#### Secondary Endpoints:

1. Patient reported NRS scores in PACU and at 24 hours
2. Patient Reported NRS scores on POD 1 and POD 3
3. Reaction to surgical subpectoral incision (signs include patient movement, tachycardia, etc.)
4. Skin assessment of sensation in PACU (axilla, distal to surgical dressing)

Normally distributed data such as the primary outcome variable will be compared using the two-sample t-test. In the case that the data are not normally distributed, the Wilcoxon rank-sum test will be used instead. Categorical variable will be compared using the Chi-Squares unless other tests such as the Fisher's exact test are more appropriate.

All endpoints will be evaluated as fits the data set with graphical figures such as scatter plots, box-and-whisker plots, and frequency histograms to visualize the distribution of these outcomes and their relationships to covariates and treatment assignment. When appropriate descriptive graphical and tabular methods will also be estimated and presented in a graphical figure.

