### CONFIDENTIAL

## Protocol Summary

Title	Pecs II Block versus Surgeon Infiltration for Open Subpectoral Biceps Tenodesis
Brief Summary	A phase IV, randomized, single-blind, single-center study measuring the effects of Pecs II block with 0.25% bupivacaine versus surgeon infiltration with 0.25% bupivacaine on postoperative pain control and opioid utilization in participants who undergo open subpectoral tenodesis.
Phase	Clinical study phase IV
Objectives	To determine if Pecs II block is superior to surgical infiltration in reduction of axillary pain after open subpectoral bicep tenodesis, especially in terms of duration.
Methodology	Phase IV, randomized, single-blind, single-center study
Endpoint	
Primary Endpoint: Opioid utilization for the first 24 hours after surgery, including during surgery, calculated as oxycodone equivalent.
 
Secondary Endpoints: Patient reported VAS scores in PACU Patient reported VAS scores on POD 1 and POD 3 Reaction to surgical subpectoral incision (signs include patient movement, tachycardia, etc.) Skin assessment of sensation in PACU (axilla, distal to surgical dressing)

Study Duration	The study will continue until 80 subjects are enrolled per arm, to allow for potential dropout and increased power.
Participant Duration	Each participant will be enrolled on DOS and complete their final follow up on postoperative day three.
Duration of IP administration	Once during surgery
Population	80 patients per study arm scheduled for open biceps tenodesis
Study Sites	NYU Langone Orthopedic Hospital and NYU Ambulatory Surgery Center at 38 th street
Number of participants	160
Description of Study Agent/Procedure	Patients in both groups will receive an interscalene nerve block with 20 mL 0.5% bupivacaine. Subjects in the Pecs II block group will receive a Pecs II fascial plane block with 20 mL 0.25% bupivacaine. The Surgical infiltration group patients will receive local infiltration of 0.25% bupivacaine by the surgeon, up to 15 mL.
Reference Therapy	Reference is Interscalene block with 0.5% bupivacaine and surgical infiltration with bupivacaine 0.25%
Key Procedures	Interscalene block with 0.5% bupivacaine, Pecs II block with 0.25% bupivacaine, local surgical infiltration with 0.25% bupivacaine

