### 1.3 Objectives and Purpose

The goal of this study is to compare the postoperative pain control using a Pecs II block with 0.25% bupivacaine to the standard of care of local surgeon infiltration with 0.25% bupivacaine following open subpectoral biceps tenodesis, particularly in terms of duration of pain control and adjunctive postoperative analgesic consumption. The primary objective will be to compare opioid utilization between the two arms within the first 24 hours after surgery, including intraoperatively, as measured by oxycodone equivalents. Our secondary objectives are measuring patient reported pain scores in PACU and at 24 hours, reaction to surgical incision, and skin assessment of sensation in the PACU.

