### POST-OPERATIVE PHASE:

After initial recruitment, subjects' pain will be assessed via visual analog scale (VAS) by nursing staff during the post-operative period as per standard of care. The VAS pain scores are collected and documented in the patient's electronic medical record. Additionally, a standardized regimen of pain medication will be given to all subjects who are enrolled. The pain medications given to patients are standard of care medications and vary based on pain level. This is determined by the clinical staff caring for each patient. While the patient is in the PACU, an authorized research member will visit the patient and obtain a pain score using the Numeric Rating Scale (NRS) and McGill Pain Scale. Skin testing in the axilla will be done in PACU prior to discharge to evaluate the presence or absence of sensation in that area. Data on PACU opioid use documented in EPIC will be collected. On POD1 and POD 3, a phone call to the patient will be made to collect additional data on oxycodone use at home as well as an NRS score at 24 and 72 hours after surgery.

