#### **4.2.3 Follow-Up Phone call (POD 1 and POD 3)**

1. Phone call to patient to collect additional data on opioid use following discharge, on POD 1 and 3 after surgery

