**1. Medication Usage Record**

Thank you for participating in our research study and helping us improve pain control for patients undergoing Open Subpectoral Biceps Tenodesis.

CONFIDENTIAL

This material is the property of the NYU School of Medicine and Langone Medical Center. Do not disclose or use except as authorized in writing by the study sponsor

**Patient:** \_\_\_\_\_

Pain medication: **Percocet**

Please record the following information in the log below:

1. Time when you take your pain medication
2. How many pills you took at each time
3. Pain score on a scale of 0-10 (0 being no pain and 10 being the worst pain imaginable)
4. Any additional pain medications (such as Advil), therapies (such as ice packs) and side effects (such as itching or nausea).

Time	Number of pills of Percocet	Pain Score (scale of 0-10)	Additional pain medications, therapy or side effects

What was your pain score on a scale from 0 to 10 (0 being no pain and 10 being the worst imaginable pain) 24 hours after the end of surgery, i.e., on \_\_\_\_\_ at \_\_\_\_\_ ?

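### Section 6.2 lists the 24-hour pain score twice, and the named tests cannot show whether the arm difference in pain changes over time

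*Combined protocol and SAP*

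**What the plan says.** Section 6.2 lists four secondary endpoints. The first is "Patient reported NRS scores in PACU and at 24 hours" and the second is "Patient Reported NRS scores on POD 1 and POD 3". Section 2.1 (Post-operative phase) says that the two follow-up calls collect "an NRS score at 24 and 72 hours after surgery".

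Other parts of the document give different sets of pain times:

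- The Protocol Summary lists PACU and "Patient reported VAS scores on POD 1 and POD 3". Each time appears once, but the scale is the VAS, not the NRS.
- Section 1.3 speaks of "measuring patient reported pain scores in PACU and at 24 hours" and leaves out POD 3.
- Section 4.2.3 describes the calls only as "Phone call to patient to collect additional data on opioid use following discharge, on POD 1 and 3 after surgery". It mentions no pain score.
- The Medication Usage Record in the attachments asks "What was your pain score on a scale from 0 to 10" and fixes the moment at 24 hours from the end of surgery. It has no matching question for 72 hours.

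In PACU, sections 2.1 and 4.1.1 describe both a VAS taken by nurses and an NRS taken by a research member.

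For continuous outcomes, sections 6.1 and 6.2 name the two-sample t test, or the rank-sum (Mann-Whitney) test if the data are not normal. The plan contains no repeated-measures model and no arm-by-time contrast, and it does not say how secondary p values are to be read. Aim 1 (section 1.1) and section 1.3 both emphasise how long pain control lasts.

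**The concern.** Two things are at stake, both in the secondary pain results.

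First, an analyst who follows the 6.2 list would fill one row for 24 hours and another for POD 1 with the same number. A reader of the report would see two pain results in agreement and take the second as support for the first, when it is a copy.

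Second, the trial wants to know whether one technique controls pain for longer. Comparing the arms at each time cannot answer that. A significant difference at 24 hours and a non-significant one at 72 hours does not show that the difference shrank; that needs a contrast between times within the same patients. The planned data support such a contrast, but the plan does not specify one.

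The gap in 4.2.3 adds a practical risk. Staff working from the visit schedule alone would not ask for pain at either call. The log has a back-up question for 24 hours but none for 72 hours.

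**Working it through.** **1. The plan's own figure.** No power, SD or correlation is given for the NRS. The only sample-size figure (section 6.3) is for opioid use: means 25 and 32 mg, SD 13, two-sided 0.05, power 0.90, 72 per group. Check: n = 2 × (1.960 + 1.282)² × 13² / 7² = 72.5, so 73 per group (74 by the exact t test). This agrees closely with 72, and nothing below touches it.

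**2. Count of pain results.** Section 6.2 lists PACU, 24 h, POD 1 and POD 3, which is four. Section 2.1 ties the two calls to 24 h and 72 h, which leaves three distinct scores.

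**3. What the duplicate does under the null.** Assume each time is tested at 0.05, the three times are independent, and the 24-h result is copied exactly.

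- Any false positive, three distinct scores: 1 − 0.95³ = 14.3%. The copy is significant only when its original is, so the figure is still 14.3% with four rows.
- At least two significant rows, no duplicate: 3 × 0.05² × 0.95 + 0.05³ = 0.00725, or 0.7%.
- At least two significant rows, with the duplicate: the 24-h test is significant (0.05), or it is not and both others are (0.95 × 0.05² = 0.0024). The sum is 0.0524, or 5.2%.

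Simulation with 1,000,000 draws, for an assumed correlation rho between the test statistics:

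| rho | any false positive (with or without the copy) | two or more rows, no duplicate | two or more rows, duplicate |
|---|---|---|---|
| 0 | 14.3% | 0.7% | 5.3% |
| 0.3 | 13.6% | 1.3% | 5.4% |
| 0.5 | 12.5% | 2.1% | 5.6% |
| 0.7 | 10.9% | 3.2% | 5.8% |

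If the call and the log give two separate 24-h records correlated 0.9 (assumed), the chance of any false positive rises a little: 15.3%, 14.1% and 12.3% at rho 0.3, 0.5 and 0.7.

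**4. What a joint model adds.** Take equal variances and a common within-patient correlation rho of 0.3 to 0.7. This range is assumed, because the documents give none.

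- *Arm difference at one time, complete data:* the same estimate and essentially the same standard error (SE) as the two-sample comparison.
- *Arm difference at 72 h, a fraction m of 72-h scores missing:* the earlier two scores explain R² = 2rho²/(1 + rho) of the variance, and the SE ratio is √(1 − m × R²). At rho 0.3 and m = 5%, R² = 0.138 and the ratio is 0.9965. At rho 0.7 and m = 20%, R² = 0.576 and the ratio is 0.9406. The SE falls by about 0.4% to 6%.
- *Change in the arm difference between two times:* SE relative to a single-time comparison is √(2(1 − rho)), which is 1.18, 1.00 and 0.77 at rho 0.3, 0.5 and 0.7. This contrast bears on duration, and separate tests do not provide it.

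**The case against.** The strongest reply is that this is a drafting slip. The Summary lists each pain time once, section 2.1 already specifies the NRS at both calls, and a careful analyst would report 24 hours once. There is a single primary endpoint, so a formal multiplicity rule for secondary endpoints is largely a matter of convention. A linear model for a bounded 0–10 score also brings an assumption that the rank-sum test avoids. All of this stands, and it is why the duplicated result *could*, not *would*, be reported twice. It does not supply the missing arm-by-time contrast or settle which times, scale and source are meant.

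Three stronger readings are tempting, and the documents do not support them.

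- *The duplicate inflates the false-positive rate.* Counting six secondary tests gives 1 − 0.95⁶ = 26.5%, but that treats the copy as an independent test. The five distinct tests give 1 − 0.95⁵ = 22.6% if independent, and less if the pain scores are positively correlated.
- *Separate tests waste precision.* An average over three times would have an SE 11% to 27% smaller than a single time (√((1 + 2rho)/3) = 0.89 to 0.73 at rho 0.7 to 0.3). The plan does not target that average, and averaging could dilute an effect that fades. At a single time with complete data the gain is essentially nil.
- *The plan orders a test of each score at 0.05.* It does not say so. Separate testing is inferred from the methods named, and 0.05 appears only in the sample-size section.

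**Conclusion.** The point holds in a limited form. Section 6.2 counts one planned measurement as two secondary endpoints. Under the null, with independent times tested at 0.05 and an exact copy, this raises the chance of two or more significant pain rows from 0.7% to about 5.2%. At an assumed correlation of 0.5 the change is from 2.1% to 5.6%. The harm is false corroboration; the chance of any false positive is not increased by an exact duplicate.

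Separately, the named methods provide no test of whether the arm difference changes from PACU to 72 hours, which the duration aim calls for. That rests on the text and on no assumed value.

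A precision gain for single-time comparisons should not be claimed. It is essentially nil with complete data and about 0.4% to 6% of the SE with 5% to 20% of 72-hour scores missing (assumed correlation 0.3 to 0.7). The primary endpoint and its sample size are unaffected. This is a cheap improvement to the secondary analysis, not a threat to the trial's main conclusion.

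**What to change.** 1. Replace items 1 and 2 of the secondary list in 6.2 with one endpoint: NRS in PACU, at 24 h (POD 1 call) and at 72 h (POD 3 call).
2. Align the Summary and section 1.3 with it. Resolve the VAS/NRS difference openly: say that the endpoint is the researcher's NRS and what use, if any, is made of the nursing VAS.
3. Add the NRS to both calls in 4.2.3.
4. State whether the call or the patient log supplies the 24-hour score, and what happens if they disagree or one is missing.
5. Prespecify one repeated-measures model with arm, time and arm-by-time terms and unstructured covariance. Report the arm difference at each time with a 95% CI, and the arm-by-time test. Keep the rank-sum test at each time as a sensitivity analysis, because the score is bounded.
6. State that secondary p values are descriptive.

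The cost is protocol wording and one extra standard model, with no new patients or measurements. The downside is a linear-model assumption for a 0–10 score, which the rank-sum sensitivity analysis is there to check.

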#### 6.2.1 Baseline Descriptive Statistics

The following patient data will be recorded: age, gender, height, weight, date of admission, date of discharge, laterality, surgical approach, implants used, duration of surgery, contamination, ASA, comorbidities (smoking, cardiac history, diabetes etc.), and medications. This information will be accessible in the patient's medical record.

### 6.3 Sample Size

80 subjects will be enrolled

Based on published reports (Reynolds et al) and our clinical experience, we estimate that patients in the Pecs group will use only 25 mg of oxycodone-equivalent, while patients receiving the infiltration will use 32 mg. Using a 2-sided, 2-sample t test, an  $\alpha$  value of 0.05 and assuming a common SD of 13, a power analysis revealed that 72 subjects were needed per group for a power of 0.90. We chose to enroll 80 subjects per arm to allow for potential dropout and an increased power.

CONFIDENTIAL

This material is the property of the NYU School of Medicine and Langone Medical Center. Do not disclose or use except as authorized in writing by the study sponsor

## 6.4 Enrollment/Randomization/Masking Procedures

We will utilize randomization.com to generate a block randomization assignments for all 160 participants. Someone that is not a stakeholder in the study will make randomization envelopes, which include the study ID number, the treatment assignment, and dosage specifics. These randomization envelopes will then be distributed to the anesthesiologist pre-operatively by the authorized researcher after informed consent is obtained.

## 6.5 Breaking the Study Blind/Participant Code

If there is any adverse event related to the drug, we will break the blind for the subject and randomization will be disclosed to the patient.

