### TREATMENT PHASE:

Patients in both groups will receive an interscalene nerve block with 20 mL 0.5% bupivacaine. Subjects in the Pecs II block group will receive 20mL 0.25% bupivacaine; 20ml will be injected between pectoralis minor and serratus anterior muscles. The subpectoral surgical skin infiltration group will receive 15mL bupivacaine 0.25% by the surgeon. These medications will be obtained from the operating room omniceil. Neither the anesthesiologist nor surgeon will be blinded to the patient's group assignment, as they are the ones administering the treatment. All other stakeholders (patient, other caregivers, and research staff collecting the data) will be blinded to the patient's group assignment.

[figure not shown]

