### 7.3.2 Relationship to Study Agent

*The clinician’s assessment of an AE’s relationship to study agent (drug, biologic, device) is part of the documentation process, but it is not a factor in determining what is or is not reported in the study. If there is any doubt as to whether a clinical observation is an AE, the event should be reported. All AEs must have their relationship to study agent assessed. In a clinical trial, the study product must always be suspect. To help assess, the following guidelines are used.*

1. **Related** – *The AE is known to occur with the study agent, there is a reasonable possibility that the study agent caused the AE, or there is a temporal relationship between the study agent and event. Reasonable possibility means that there is evidence to suggest a causal relationship between the study agent and the AE.*
2. **Not Related** – *There is not a reasonable possibility that the administration of the study agent caused the event, there is no temporal relationship between the study agent and event onset, or an alternate etiology has been established.*

*For all collected AEs, the clinician who examines and evaluates the participant will determine the AE’s causality based on temporal relationship and his/her clinical judgment. The degree of certainty about causality will be graded using the categories below.*

1. **Definitely Related** – *There is clear evidence to suggest a causal relationship, and other possible contributing factors can be ruled out. The clinical event, including an abnormal laboratory test result, occurs in a plausible time relationship to drug administration and cannot be explained by concurrent disease or other drugs or chemicals. The response to withdrawal of the drug (dechallenge) should be clinically plausible. The event must be pharmacologically or phenomenologically definitive, with use of a satisfactory rechallenge procedure if necessary.*
2. **Probably Related** – *There is evidence to suggest a causal relationship, and the influence of other factors is unlikely. The clinical event, including an abnormal laboratory test result, occurs within a reasonable time after administration of the drug, is unlikely to be attributed to concurrent disease or other drugs or chemicals, and follows a clinically reasonable response on withdrawal (dechallenge). Rechallenge information is not required to fulfill this definition.*

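### Section 6.5 tells the patient the arm after any drug-related adverse event, whatever the need or timing, and so can unblind the person who takes and reports part of the primary endpoint

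*Combined protocol and SAP*

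**What the plan says.** Section 6.5 is a single sentence. Its trigger is a drug-related adverse event of whatever kind, and its consequence is: "we will break the blind for the subject and randomization will be disclosed to the patient". It gives no threshold of severity, does not ask whether disclosure is needed for care, and sets no time relative to data collection. No other section limits the rule, asks for a record of disclosures, or says how unblinded patients are analysed.

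Section 2.1 (treatment phase) sets out the blinding: "All other stakeholders (patient, other caregivers, and research staff collecting the data) will be blinded". The exceptions are the two clinicians who give the treatments: "Neither the anesthesiologist nor surgeon will be blinded". Section 6.1 rests its intention-to-treat rationale on the patient not knowing the intervention.

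The primary endpoint (section 6.2) is opioid use from surgery to 24 hours in oxycodone equivalents. PACU use comes from the electronic record (sections 2.1 and 4.1.1). For the period after discharge, section 2.1 (post-operative phase) provides for contact on the first and third postoperative days: "a phone call to the patient will be made to collect additional data on oxycodone use at home as well as an NRS score". The scores are for 24 and 72 hours. The attached Medication Usage Record asks the patient to log pills and pain scores.

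For relatedness, the two-way definition in section 7.3.2 lists several alternative grounds for calling an event related. One of them is that "there is a temporal relationship between the study agent and event". The same section then bases causality on timing together with clinical judgment and adds a five-level scale. Section 6.5 does not say which of these applies.

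**The concern.** The home part of 24-hour opioid use is exposed to knowledge of the arm in two ways: the patient decides how many pills to take, and the patient reports the number. Someone told that they did, or did not, receive the block may change either. The NRS scores by phone are open to the same influence, and an unblinded patient may reveal the arm to the caller.

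The trigger is an event after randomization whose frequency may differ between arms, so any effect need not cancel. Because timing alone can satisfy the two-way definition of relatedness, minor events in PACU could lead to disclosure. With no log, the number of patients unblinded before 24 hours could not be established afterwards, and neither could the possible effect on the result.

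**Working it through.** **Inputs from the plan (section 6.3).** Means of 25 mg (Pecs II) and 32 mg (infiltration), so a target difference of 7 mg; SD 13 mg; two-sided alpha 0.05; 72 per group for power 0.90; 80 per arm enrolled.

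**The plan's own figure.** n per group = 2 × (13/7)² × (1.960 + 1.282)² = 6.898 × 10.51 = 72.5, so 73 by the normal approximation. The t-test solution is 73.45, so 74. The stated 72 is reproduced within two patients. Power at 80 per arm is 0.926 (normal) or 0.923 (t). The sample size is not in question here.

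**Precision.** SE of the difference at 80 per arm = 13 × √(2/80) = 2.06 mg.

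**Which part of the endpoint is exposed.**
- Intraoperative use precedes disclosure, and PACU use is read from the record. Neither depends on what the patient reports.
- Home use within 24 hours is exposed if disclosure comes before it is taken or reported.
- An event first found at or after the POD 1 call, taken as falling at about 24 hours, comes too late to change 24-hour intake. Later disclosure can still affect what is reported on POD 3.

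**Bias formula.** Let f be the share of an arm told before reporting, and s the mean shift in 24-hour use among those told. Bias = f(infiltration) × s(infiltration) − f(Pecs II) × s(Pecs II). If only one arm shifts, its size is f × s. Equal shifts in the same direction with equal shares would cancel; equal and opposite ones would double the one-arm figure. The documents support neither assumption, so the one-arm case is shown.

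**Assumed range.** The documents give neither f nor s. I take f from 1% to 30% and s from 3.5 mg (half the target) to 7 mg (all of it).

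| Share told | Patients of 80 | Bias at 3.5 mg | Bias at 7 mg | Share of 7 mg target |
|---|---|---|---|---|
| 1% | 0.8 | 0.035 mg | 0.07 mg | 0.5% to 1% |
| 5% | 4 | 0.175 mg | 0.35 mg | 2.5% to 5% |
| 30% | 24 | 1.05 mg | 2.1 mg | 15% to 30% |

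**Effect on the test.** At 80 per arm (normal approximation), a bias B gives a type I error of Φ(−1.96 − B/2.06) + 1 − Φ(1.96 − B/2.06). If it runs toward the null, power is Φ((7 − B)/2.06 − 1.96).

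| Bias | Type I error | Power if toward the null |
|---|---|---|
| 0.05 mg | 0.050 | 0.922 |
| 0.5 mg | 0.057 | 0.885 |
| 1.0 mg | 0.078 | 0.831 |
| 2.0 mg | 0.16 | 0.682 |

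**The case against.** The strongest reply is that the rule will seldom operate. Section 5.1 describes the risk of toxicity and of procedural complications as low or very low. Section 7.6 expects few serious events, and the events it names for review are allergy, intravascular injection and infection at the site. At 1% disclosure the bias is at most 0.07 mg and the type I error is unchanged. The upper shift of 7 mg is also generous: it attributes the whole assumed treatment effect to knowledge alone, although only home use after disclosure can move. Both points stand, which is why the range begins at 1% and the upper end is not a forecast.

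Three stronger readings are tempting, and the documents do not support them.

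- *Disclosure always comes before the calls.* Section 6.5 gives no time. Section 7.4 has adverse events sought at each visit and non-serious ones recorded until 7 days after participation ends, so some disclosures would come after the 24-hour window.
- *Any event close in time to the injection must trigger disclosure.* The two-way definition permits that reading, but section 7.3.2 also calls for clinical judgment and treats an established alternative cause as grounds for not related. Minor events could trigger the rule; the text does not say that they will.
- *Telling the patient adds nothing, because the anesthesiologist and surgeon already know the arm.* Other caregivers are blinded, and an event may arise after discharge. Whether disclosure helps care is a clinical judgment, and a revised rule must leave room for it.

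What survives is that the rule makes disclosure automatic even when care does not need it and the outcome data are still to come.

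**Conclusion.** The concern holds as a limited one. The rule in section 6.5 conflicts with the patient blinding in section 2.1 and with the rationale in section 6.1. When disclosure falls before the 24-hour window closes, or before the POD 1 or POD 3 report, it can bias home opioid use and NRS scores.

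Under the assumed range, the bias in the primary comparison is about 0.04 to 2.1 mg, against a 7 mg target and a standard error of 2.06 mg. It is negligible if drug-related events are rare, as the protocol's risk language suggests, and material only if the trigger is applied broadly. Direction is unknown: it depends on patients' expectations and on how events divide between arms. A reader might infer that the primary result will be materially biased; the documents give no event rate or reporting shift that would support this. The case for changing the rule is that the risk is avoidable at little cost and, without a log, could not be assessed later.

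**What to change.** Rewrite section 6.5 as follows.

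1. Before the POD 3 call, disclose the assignment to the patient or to blinded staff only when the treating clinician judges that knowing it is needed for that patient's care. Otherwise disclose it after that call. Need for care then replaces relatedness as the trigger, so section 6.5 no longer depends on which scale in section 7.3.2 is used.
2. Keep the person making the outcome calls blinded after any disclosure.
3. Log the date, time, reason and arm of each disclosure, with access to the log withheld from the outcome caller.

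Add to section 6.2:

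4. Keep all unblinded patients in the primary ITT analysis, and report by arm how many were unblinded before 24 hours.
5. As a supportive analysis, vary the self-reported home use of those patients over a range of shifts set separately by arm (for example, 0 to 7 mg in either direction, with home use not below zero), and report how the arm difference changes. Do not exclude them or stratify on unblinding: it follows randomization and may differ by arm, so either step could itself bias the comparison.

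The cost is one rewritten paragraph, one log and one short pre-specified analysis. The sample size does not change. The downside is that some patients learn their arm up to about three days later.
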